14.8. Appendix 8: Abbreviations & Trade Marks

14.8.1. Abbreviations

Abbreviation	Description
%AUCex	Percentage of AUC(0-¥) obtained by extrapolation
μg	Microgram
A&R	Analysis and Reporting
ABC	airway, breathing, and circulation from Basic Life Support
aCCR4	Anti C-C chemokine receptor type 4
ADA	Anti-drug antibody
ADA	Anti-drug antibodies
ADCC	Antibody Dependent Cell Cytotoxicity
AE	Adverse Event
AIC	Akaike's Information Criteria
ALT	Alanine aminotransferase (SGPT)
AST	Aspartate aminotransferase (SGOT)
AUC	Area under the concentration-time curve
	Area under the concentration-time curve from time zero (pre-dose)
$AUC(0-\infty)$	extrapolated to infinite time
	Area under the concentration-time curve from time zero (pre-dose) to
	last time of quantifiable concentration within a subject across all
AUC(0-t)	treatments
	Area under the concentration-time curve from zero (pre-dose) to some
AUC(0-x)	fixed nominal time x
BCG	Bacillus Calmette Guérin vaccine
BMI	Body mass index
BSA	Body surface area
CFB	Change from baseline
CI	Confidence Interval
CL	Systemic clearance of parent drug
Cmax	Maximum observed concentration
CMV	Cytomegalovirus
CPK	Creatine phosphokinase
CPMS	Clinical Pharmacology Modelling and Simulation
CPR	Cardio-Pulmonary Resuscitation
CPSSO	Clinical Pharmacology Sciences and Study Operations
CRF	Case Report Form
CRP	C-Reactive Protein
CS	Clinical Statistics
CSR	Clinical Study Report
CTLA	Cytotoxic T-Lymphocyte Antigen
CTR	Clinical Trial Register
CVb / CVw	Coefficient of Variation (Between) / Coefficient of Variation (Within)
CXCR	CXC Chemokine Receptor
DC	Dendritic Cells

Abbreviation	Description
DEC	Dose Escalation Committee
DMPK	Drug Metabolism and Pharmacokinetics
DOB	Date of Birth
DP	Decimal Places
DPT	Diphtheria, pertussis, tetanus
DTH	Delayed type hypersensitivity
EBV	Epstein-Barr Virus
ECG	Electrocardiogram
ECL	Immunoelectrochemiluminescent
eCRF	Electronic Case Record Form
EDTA	Ethylenediaminetetraacetic acid
EMA	European Medicines Agency
FCS	Foetal Calf Serum
FDA	
FDAAA	Food and Drug Administration
	Food and Drug Administration Clinical Results Disclosure Requirements
FTIH	First Time In Human
GCP	Good Clinical Practice
G-CSF	Granulocyte-Colony Stimulating Factor
GGT	Gamma glutamyltransferase
GI	Gastrointestinal
GLP	Good Laboratory Practice
GSK	GlaxoSmithKline
h	Hour
HBcAb	Hepatitis B core antibody
HBsAg	Hepatitis B surface antigen
Нер В	Hepatitis B
Hep C	Hepatitis C
HIV	Human Immunodeficiency Virus
HRT	Hormone Replacement Therapy
HSV	Herpes Simplex Virus
IA	Interim Analysis
IB	Investigator's Brochure
ICH	International Conference on Harmonization
ICU	Intensive Care Unit
ID	Intradermal
IDMC	Independent Data Monitoring Committee
IDSL	Integrated Data Standards Library
IEC	Independent Ethics Committee
IFN-γ	Interferon-gamma
Ig	Immunoglobulin
IgM	Immunoglobulin M
IHC	Immunohistochemistry
ii TAU	Immuno-Inflammation Therapeutic Area Unity
IL2R	Interleukin 2 Receptor
ILH	Immediate local hypersensitivity

Abbreviation	Description
IMMS	International Modules Management System
INR	International Normalised Ratio
IP	Investigational Product
kg	Kilogram
L	Litres
LAG-3	Lymphocyte Activation Gene 3
LAG-3	Lower Limit of Quantification
	`
mg ml	Milligram Millilitre
MlU/mL	milli-international units per millilitre
mm	Millimetre
MMR	Measles, mumps, rubella
MMRM	Mixed Model Repeated Measures
mRNA	Messenger Ribonucleic Acid
MRT	Mean Residence Time
NK	Natural Killer
nM	Nanomolar
NOAEL	No Observed Adverse Effect Level
PASI	Psoriasis Area Severity Index
PBMC	Peripheral Blood Mononuclear Cell
PCI	Potential Clinical Importance
PD	Pharmacodynamic
PDMP	Protocol Deviation Management Plan
PGA	Physicians Global Assessment
PK	Pharmacokinetic
PLSS	Plaque Lesional Severity Score
PPD	Tuberculin Purified Protein Derivative
QTc	Electrocardiogram QT interval corrected for heart rate
QTcB	Bazett's QT Interval Corrected for Heart Rate
QTcF	Frederica's QT Interval Corrected for Heart Rate
RAP	Reporting and Analysis Plan
RBC	Red blood cells
RNA	Ribonucleic acid
RO	Receptor Occupancy
RT-PCR	Reverse transcription polymerase chain reaction
SAC	Statistical Analysis Complete
SAE	Serious adverse event(s)
SGOT	Serum glutamic-oxaloacetic transaminase
SGPT	Serum glutamic pyruvic transaminase
sLAG-3	Soluble Lymphocyte Activation Gene 3
SOP	Standard Operation Procedure
SPC	Summary of Product Characteristics
SPM	Study Procedures Manual
$t^{1/2}$	Terminal phase half-life
TA	Therapeutic Area
171	Therapeutic Area

Abbreviation	Description
TB	Tuberculosis
TFL	Tables, Figures & Listings
tlast	Time of last quantifiable concentration
tmax	Time of occurrence of Cmax
UK	United Kingdom
USA	United States of America
Vss	Volume of distribution at steady state
VZV	Varicella Zoster Virus
WBC	White blood cells
λz	Terminal elimination rate

14.8.2. Trademarks

Trademarks of the GlaxoSmithKline Group of Companies	
ADVAIR	

Trademarks not owned by the GlaxoSmithKline Group of Companies
NONMEM
SAS
WinNonlin

14.9. Appendix 9: List of Data Displays

14.9.1. Data Display Numbering

The following numbering will be applied for RAP generated displays:

Section	Tables	Figures
Study Population	1.1 to 1.14	Not applicable
Efficacy	2.1 to 2.23	2.1 to 2.n
Safety	3.1 to 3.35	3.1 to 3.6
Pharmacokinetic	4.1 to 4.6	4.1 to 4.6
Population Pharmacokinetic (PopPK)	Not applicable	Not applicable
Pharmacodynamic and / or Biomarker	6.1 to 6.14	6.1 to 6.18
Pharmacokinetic / Pharmacodynamic	Not applicable	Not applicable
Section	List	ings
ICH Listings	1 to	31
Other Listings	32 t	o 63

14.9.2. Mock Example Shell Referencing

Non IDSL specifications will be referenced as indicated and if required example mock-up displays provided in Example Mock Shells for Data Displays.

Non-Standard displays are indicated in the 'IDSL / TST ID / Example Shell' column as 'Reference.'

Section	Figure	Table	Listing
Study Population	POP_Fn	POP_Tn	POP_Ln
Efficacy	EFF_Fn	EFF_Tn	EFF_Ln
Safety	SAFE_Fn	SAFE_Tn	SAFE_Ln
Pharmacokinetic	PK_Fn	PK_Tn	PK_Ln
Population Pharmacokinetic (PopPK)	POPPK_Fn	POPPK_Tn	POPPK_Ln
Pharmacodynamic and / or Biomarker	PD_Fn	PD_Tn	PD_Ln
Pharmacokinetic / Pharmacodynamic	PKPD_Fn	PKPD_Tn	PK/PD_Ln

14.9.3. Deliverables

Following review of the IA2 and IA W2 outputs and finalisation of the database, the final list of outputs to be re-run at SAC will be reviewed.

Delivery	Description
IA1	Interim Analysis 1 Statistical Analysis Complete
IA2 EFF Interim Analysis 2 Statistical Analysis Complete for Efficacy endpoints	
IA2 Interim Analysis 2 Statistical Analysis Complete	
IA2 W2 Interim Analysis 2 Wave 2 Statistical Analysis Complete	
SAC	Final Statistical Analysis Complete

14.9.4. Study Population Tables

Study	Study Population Tables					
No.	Population	IDSL / Example Shell	Title	Programming Notes	Deliverable	
Subjec	t Disposition			•	•	
1.1.	safety	ES1	Summary of subject disposition for healthy volunteers	by treatment group - 8 groups	IA1 IA2 W2	
1.2.	safety	ES1	Summary of subject disposition for psoriasis patients	Same as for HV - 4 groups	IA2W2	
1.3.	All screened	ES6	Summary of reasons for screen failures for healthy volunteers	Not by treatment group	SAC	
1.4.	All screened	ES6	Summary of reasons for screen failures for psoriasis patients	Same as for HV	SAC	
Protoc	ol Deviation					
1.5.	Safety	DV1A	Summary of important protocol deviations for healthy volunteers	by treatment group - 8 groups	SAC	
1.6.	Safety	DV1A	Summary of important protocol deviations for psoriasis patients	Same as for HV - 4 groups	SAC	
Popula	ation Analysed			•		
1.7.	All screened	SA1	Summary of study populations for healthy volunteers	by treatment group - 8 groups See text for screen failures	IA2 W2	
1.8.	All screened	SA1	Summary of study populations for psoriasis patients	Same as for HV - 4 groups See text for screen failures	IA2 W2	

Study	Population Tab	les			
No.	Population	IDSL / Example Shell	Title	Programming Notes	Deliverable
Demog	raphic and Bas	eline Characteris	tics		•
1.9.	safety	DM1	Summary of demographic characteristics for healthy volunteers	 by treatment group - 8 groups Include: Gender, height, weight and BMI Include age category: <18 years, 18 to 65 years, 66 to 75 years and >75 years 	IA2 W2
1.10.	safety	DM1	Summary of demographic characteristics for psoriasis patients	Same as for HV - 4 groups	IA2 W2
1.11.	safety	DM5	Summary of race and racial combinations for healthy volunteers	 by treatment group - 8 groups Report only categories where n>0 count 	SAC
1.12.	safety	DM5	Summary of race and racial combinations for psoriasis patients	Same as for HV - 4 groups	SAC
1.13.	safety	DM11	Summary of age ranges for healthy volunteers	by treatment group - 8 groups	SAC
1.14.	safety	DM11	Summary of age ranges for psoriasis patients	by treatment group - 4 groups	SAC

14.9.5. Efficacy Tables

Efficac	y: Tables				
No.	Population	IDSL / Example Shell	Title	Programming Notes	Deliverable
DTH inc	duration				
2.1.	Safety		Summary of induration diameter for healthy volunteers (DTH subjects)	 Absolute and CFB by challenge site (4) and overall => 5 parameters 2 treatment groups (cohort placebo (DTH) and 0.15mg (DTH=ADA-ve) 	IA1
2.2.	Safety		Summary results of statistical analysis of change from baseline in induration diameter for healthy volunteers (DTH subjects)	1. for overall only (1 parameter) 3. 2 treatment groups (cohort 5): placebo (DTH) and 0.15mg (DTH=ADA-ve)	IA1
2.3.	safety		Summary of duration of induration for healthy volunteers (DTH subjects)	1. Absolute 2. 2 treatment groups: placebo (DTH) and 0.15mg (DTH=ADA-ve) 3. If needed for SAC, include only the summary of observed duration (no HR estimate)	IA1
BSA					
2.4.	Safety		Summary of body surface area by visit for psoriasis patients	 Absolute, CFB, %CFB 4 regional BSA Total BSA (sum of the 4 regional BS) 	SAC

Efficac	/: Tables				
No.	Population	IDSL / Example Shell	Title	Programming Notes	Deliverable
PASI					
2.5.	Safety	TE1	Summary of PASI scores by visit for psoriasis patients	 By treatment group - 4 groups Absolute, CFB, %CBF (byline) 	IA2 EFF
2.6.	Safety	TE2	Summary of PASI50 and PASI75 responders by visit for psoriasis patients	 By treatment group - 4 groups PASI50/75 Footnote: PASI50 or PASI75 responders are patients with a ≥ 50% or 75% reduction in PASI score from baseline 	IA2 EFF
2.7.	Safety	TE3	Summary of statistical analysis results for change from baseline in PASI scores over time for psoriasis patients		IA2 EFF
PLSS					
2.8.	Safety	TE1	Summary of PLSS scores by visit for psoriasis patients	 Same table as for PASI Index and biospy lesions (byline) Absolute, CFB, %CBF (byline) 	IA2 EFF
2.9.	Safety	TE3	Summary of statistical analysis results for change from baseline in PLSS scores over time for psoriasis patients	 Same as for PASI Index lesion only CFB 	IA2 EFF

Efficacy	: Tables				
No.	Population	IDSL / Example Shell	Title	Programming Notes	Deliverable
PGA					
2.10.	Safety	TE1	Summary of PGA scores by visit for psoriasis patients	 Absolute, CFB Considers categories as continuous 	IA2 EFF
2.11.	Safety	TE2	Summary of PGA responders by visit for psoriasis patients	Same table as for PASI50/75 (include exact CI) Footnote: definition of PGA responders	IA2 EFF
2.12.	Safety	TE4	Summary of PGA responses by visit for psoriasis patients	Frequency count (categorical variable)	IA2 EFF
Endpoi	nts for go/no g	o decisions			
2.13.	Safety		Bayesian analyses of key endpoints	See Section 13 IA2 EFF: PASI and PLSS IA2: total LAG3 cells, Ki67, epidermis thickness Need to add SAS log + CV plots	IA2 EFF IA2

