Protocol Activity		st lenge					In C	linic Per	iod								Out P	atient	Visits	5			
			Day 28			Day	29 (Day ′	1)		Day 30 (Day 2 post- dose)		Day 32 (Day 4 post- dose)											
	Day 1	Day 3	Day 28	Pre- dose	0 hour	2 hour post- infusion start	4 hour post- infusion start	post-	post-	24 hour post- infusion start	48 hours post- infusion start	start	(Day 8 post-	11 post-	15 post-		22 post-	25 post-	29 post-		Day 85 (Day 57 post- dose)		121 post-
Window			±3d										±1d	±1d	±1d	±1d	±1d	±1d	±1d	±2d	±2d	±2d	±3d
Efficacy Assessn	nents																						
Visual Arm Inspection	Xď									Xe													
ID PPD Challenge	Xf									Xf													
Bleb/ILH Assessment	Xe									Xe													
Ball Point Pen Technique		х										х	х		Х		Х						
Skin Biopsy		Xg										Xg											

CONFIDENTIAL

Protocol Activity	1 Chal	st lenge					In C	linic Per	iod								Out P	atient	Visits	;			
			Day 28			Day	29 (Day 1	1)		Day 30 (Day 2 post- dose)	Day 31 (Day 3 post- dose)	Day 32 (Day 4 post- dose)											
	Day 1	Day 3	Day 28	Pre- dose	0 hour	2 hour post- infusion start	4 hour post- infusion start	post-	post-	24 hour post- infusion start	48 hours post- infusion start	72 hour post- infusion start	(Day 8 post-		15 post-	18 post-		25 post-	29 post-		Day 85 (Day 57 post- dose)		
Window			±3d										±1d	±1d	±1d	±1d	±1d	±1d	±1d	±2d	±2d	±2d	±3d
Laboratory Asses		nts		-						-						-						-	
Haematology			Х					Х	Х			Х	Х	Х	Х	Х	Х	Х	Х	Х	Х	Х	Х
Chemistry	X ^h		Х					Xi	Xi			Х	Х		Х		Х		Х	Х	Х	Х	Х
Urinalysis	Xh		Х					Х	Х			Х	Х		Х		Х		Х	Х	Х	Х	Х
CMV and EBV serology sample			Х																				
Viral load sample (CMV, EBV, HSV, VZV) ^j			х																				
Immunogenicity Sample				Х									Х						Х			Х	
PK Sample ^k					◀																>	-	
Immune Cell Phenotyping ⁱ				Х				Х		Х		Х	Х		Х				Х		Х	Х	х
CD16 and LAG-3 Receptor occupancy				х				Х		х		х	х		Х				Х		Х	х	x
Cytokine Sample				Х				Х	Х	Х	Х												
G-CSF Sample				Х				Х		Х		Х	Х		Х				Х	Х	Х	Х	Х

CONFIDENTIAL

Protocol Activity	1 Chal	st lenge					In C	linic Per	iod								Out P	atient	Visits	;			
			Day 28			Day	29 (Day ′	1)		Day 30 (Day 2 post- dose)	Day 31 (Day 3 post- dose)	Day 32 (Day 4 post- dose)											
	Day 1	Day 3	Day 28	Pre- dose	0 hour	2 hour post- infusion start	4 hour post- infusion start	post-	post-	24 hour post- infusion start	48 hours post- infusion start	start	(Day 8 post-	11 post-	15 post-	18 post-	22 post-	25 post-		43 post-		Day 113 (Day 85 post- dose)	

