6.3.5.2. Follow-up of healthy volunteers who exhibit reduction of PPD challenge

Healthy volunteers will undergo a first PPD DTH ID challenge on Day 1 and then on Day 30 (24 hours post GSK2831781 infusion) as described in Section 3.2. Healthy volunteers who produce an induration of ≥ 6 mm in the post dose challenge, will not require further PPD DTH ID re-challenges. However, subjects who produce a DTH induration of < 6 mm (i.e. exhibit reduction), will have a PPD DTH ID re-challenge after a further 3 months. If they still produce an induration of < 6 mm, it is likely that they will be PPD ID re-challenged every 3 months until the DTH induration is ≥ 6 mm dependent on review by the DEC.

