5.2. Baseline Definitions

For all endpoints (except as noted in baseline definitions) the baseline value will be the latest pre-dose assessment with a non-missing value, including those from unscheduled visits. If time is not collected, Day 1 assessments are assumed to be taken prior to first dose and used as baseline.

Unless otherwise stated, if baseline data is missing no derivation will be performed and baseline will be set to missing.

Table 2 Baseline Definitions - SAFETY ENDPOINTS

	Study assessments considered as baseline			Baseline used in data display		
Parameter ¹	Screening Day -1		Day 1 (pre- dose)			
Healthy Volunteers (No DTH)						
12 Lead ECG & Vital Signs	X	Χ	Χ	Day 1 (pre-dose)		
Lab results	Х	Χ		Day -1		
Cytokine			Χ	Day 1 (pre-dose)		
Psoriasis patients				•		
Vitals Signs	Х	Χ	Χ	Day 1 (pre-dose)		
12-Lead ECG	Х		Χ	Day 1 (pre-dose)		
Lab results	Х	Х		Day -1		
Cytokines			Χ	Day 1 (pre-dose)		

	Study a	assessments			
Parameter ¹	Day -26 Day -24		Day 1 (pre- dose)	Baseline used in data display	
Healthy Volunteers (DT	H)				
Vitals Signs	Χ	X		X	Day 1 (pre-dose)
12-Lead ECG	Х			X	Day 1 (pre-dose)
Lab results	Х		Х		Day -1
Cytokines				X	Day 1 (pre-dose)

Table 3 Baseline Definitions – EFFICACY / PHARMACODYNAMIC AND BIOMARKER ENDPOINTS

Parameter	Visit considered as baseline		Baseline used for data	
	Day -1	Day 1 (pre-dose)	displays	
Healthy Volunteers (No DTH)				
Flow cytometry		X	Day 1 (pre-dose)	
G-CSF		X	Day 1 (pre-dose)	
sLAG-3		X	Day 1 (pre-dose)	
Blood transcriptomics		X	Day 1 (pre-dose)	
Psoriasis patients				
PBSA	Х		Day -1	
PASI	X		Day -1	
PLSS	X		Day -1	
PGA	X		Day -1	
Flow cytomery		X	Day 1 (pre-dose)	
G-CSF		X	Day 1 (pre-dose)	
sLAG-3		X	Day 1 (pre-dose)	
Blood transcriptomics		X	Day 1 (pre-dose)	
Skin Biopsy (transcriptomics)	X		Day -1	

Visit consid	ered as base	line		Baseline used for data					
Challenge DTH Day -26	Challenge DTH Day -24	Challenge DTH Day - 1	Challenge DTH Day 1 (pre-dose)	displays					
TH)									
X	X			DTH Day -24 if 2 assessments DTH Day -26 if only 1 assessment (see footnote)					
			Χ	DTH Day 1 (pre-dose)					
			Χ	DTH Day 1 (pre-dose)					
			Χ	DTH Day 1 (pre-dose)					
			Х	DTH Day 1 (pre-dose)					
Х				DTH Day -26					
	Challenge DTH Day -26 TH)	Challenge DTH DTH Day -26 Day -24 TH) X X	DTH DTH DTH DAY - Day -26 Day -24 1 TH) X X	Challenge DTH DTH DTH DTH Day 1 (pre-dose) TH) X X X X X X X X					

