8. EFFICACY ANALYSES

8.1. DTH Induration (only for HV)

8.1.1. Endpoint / Variables

- The induration diameter (mm) by challenge site is defined as the average of the 2 skin response test values (vertical and horizontal) at each challenge site.
 A challenge site is defined by skin response (SR) directionality (upper/lower) and SR laterality (left/right). There are 4 categories:
 - Left upper
 - Right upper
 - Left lower
 - Right lower
- 2. The overall induration diameter (mm) is defined as the average of the non-missing induration diameters over the challenge sites.
- 3. The duration of induration is the time (in days) to achieve an overall induration less than 6mm from baseline (see Section 5.2 for baseline definition). It will be calculated as: Date of 1st overall induration < 6mm Date of baseline induration assessment + 1. For these subjects who do not achieve an overall induration less than 6mm from the time of the PPD re-challenge post dose, the duration of induration is calculated as time from the PPD re-challenge post dose up to the last available induration measurement +1.

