8.1.4.1. Statistical Methodology Specification

Endpoint

Change from baseline in induration diameter (mm) (Overall induration diameter only)

Model Specification

- Mixed models repeated measures (MMRM) model.
- Terms fitted in the MMRM model will include:
 - Fixed categorical covariates: Treatment, day (visit), treatment * day (visit) interaction
 - Fixed continuous covariates: Baseline (see Section 5.2 for baseline definition)
 - Repeated: Day (visit)
- An unstructured covariance will be used to account for the within-subject correlation. by specifying 'type=UN' on the REPEATED line.
- The Kenward and Roger method for approximating the denominator degrees of freedom and correcting for bias in the estimated variance-covariance of the fixed effects will be used.
- LSmeans of the CFB will be calculated using the observed margins (OM argument added in the LSmeans function)

Model Checking & Diagnostics

 In the event that this model fails to converge, alternative correlation structures may be considered.

Model Results Presentation

Table/Figure of the LS means and 95% CI (by treatment and visit)

Endpoint / Variables

Duration of induration of at least 6mm (days)

Model Specification

Hasard ratios will be estimated using the Pike estimator.

Model Results Presentation

- Summary table of the hazard ratios
- No plot

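### Indurations still at or above 6 mm at the last reading enter Table 2.3 as completed durations with no censoring flag, and a final-analysis version of the table would also drop the hazard ratio

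*SAP*

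**What the plan says.** How long the induration lasts after re-challenge is a listed secondary endpoint (Protocol 2; SAP 2.2), assessed in the DTH cohort of 6 active and 6 placebo subjects.

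- **Subjects who resolve.** SAP 8.1.1 item 3 defines the duration as "time (in days) to achieve an overall induration less than 6mm from baseline". The formula subtracts the "Date of baseline induration assessment + 1".
- **Subjects who do not resolve.** In the same item, "the duration of induration is calculated as time from the PPD re-challenge post dose up to the last available induration measurement +1".
- **Baseline.** SAP 5.2, Table 3, takes the induration baseline as "DTH Day -24 if 2 assessments DTH Day -26 if only 1 assessment (see footnote". Both days belong to the first challenge, before dosing.
- **Summary.** SAP 8.1.2 lists the duration as an absolute value, and 8.1.4 applies descriptive statistics to it. Neither section mentions censoring.
- **Effect estimate.** SAP 8.1.4.1 states: "Hasard ratios will be estimated using the Pike estimator". It defines no event indicator.
- **Display.** Table 2.3 (SAP 14.9.5) is listed for the first interim analysis (IA1). Its third programming note says that a version needed for the final analysis (SAC) should "include only the summary of observed duration (no HR estimate".

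**The concern.** A reaction still present at the last reading has a duration known only to be at least that long. Recording it as finished loses that information in two ways. A subject with a large induration who misses later visits looks like one whose reaction was suppressed early. A subject who stays above 6 mm throughout looks like one who resolved at the final visit.

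The trial's hypothesis is that depleting LAG-3+ cells reduces the DTH reaction, so unresolved reactions would be expected mainly on placebo, where this scoring does most harm. The hazard ratio could handle such times properly, but it is the item omitted from any final-analysis version of the table. With 6 subjects per arm, one or two unresolved subjects move an arm's summary. The plan relies on estimation without formal hypotheses, so the summary is itself the result.

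**Working it through.** **Inputs**

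- Re-challenge on study Day 30. Protocol 6.3.5.2: "Healthy volunteers will undergo a first PPD DTH ID challenge on Day 1 and then on Day 30 (24 hours post GSK2831781 infusion".
- Readings from the "Ball Point Pen Technique" row of the DTH table in Protocol 6.1: study Days 32, 36, 43 and 50, which are post-dose Days 4, 8, 15 and 22. Outpatient visits have a window of ±1 day.
- Study day = post-dose day + 28, which agrees with the paired labels in that table (8/36, 15/43, 57/85).
- Baseline at DTH Day −26 or −24, which is study Day 3 or Day 5.
- The documents give no induration durations, so the 6 v 6 data sets below are assumed.

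**Step 1. Value given to a subject who never resolves**

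- Read through Day 50: 50 − 30 + 1 = 21 days (20 to 22 with the visit window).
- Last read at post-dose Day 8 (study Day 36): 36 − 30 + 1 = 7 days.

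**Step 2. Value given to a subject who resolves**

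| First reading below 6 mm | From re-challenge (Day 30) | As written, baseline Day 3 | As written, baseline Day 5 |
|---|---|---|---|
| Day 32 | 3 | 30 | 28 |
| Day 36 | 7 | 34 | 32 |
| Day 43 | 14 | 41 | 39 |
| Day 50 | 21 | 48 | 46 |

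On a single clock from the re-challenge, 21 days covers both a resolver at the last reading and a subject who never resolves. As written, every resolver (28 to 48 days) scores longer than every non-resolver (21 days) at nominal visits.

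**Step 3. Effect on arm means.** Assume that 3 placebo subjects resolve on Day 43 and 3 never resolve, that all 6 active subjects resolve on Day 36, and that baseline is Day 3.

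- One clock: placebo (3×14 + 3×21)/6 = 17.5; active 7.0; active − placebo = −10.5 days.
- If the three unresolved reactions really lasted 28 days, placebo would be (3×14 + 3×28)/6 = 21.0 and the difference −14.0 days.
- As written: placebo (3×41 + 3×21)/6 = 31.0; active 34.0; difference +3.0 days. The sign is reversed.

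**Step 4. Effect on the median.** If 4 of 6 placebo subjects never resolve and all are read through Day 50, the descriptive median on one clock is 21 days. The Kaplan-Meier curve never falls below 4/6 = 0.67, so its median is not reached.

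**Step 5. Effect on the hazard ratio.** Pike estimator: HR = (O_A/E_A)/(O_P/E_P), for resolution. Assume placebo resolves on Days 36, 43 and 43 with 3 unresolved, and active resolves 5 on Day 36 and 1 on Day 43.

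- One clock, unresolved censored at 21. At 7 days there are 6 events with 6 v 6 at risk, so E is 3 in each arm. At 14 days there are 3 events with 5 placebo and 1 active at risk, so E_P = 2.5 and E_A = 0.5. HR = (6/3.5)/(3/5.5) = 3.14.
- One clock, no flag, so the 3 unresolved count as events at 21. This adds 3 to both O_P and E_P. HR = (6/3.5)/(6/8.5) = 2.43.
- As written, unresolved censored at 21. They leave the risk set before any resolver's event. At 34 days there are 6 events with 3 placebo and 6 active at risk, so E_P = 2 and E_A = 4. At 41 days there are 3 events with 2 and 1 at risk, so E_P = 2 and E_A = 1. HR = (6/5)/(3/4) = 1.60.

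Both the flag and the time origin therefore change the hazard ratio. Keeping it without correcting the origin leaves it distorted.

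**The case against.** The other side has real points.

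- **The hazard ratio is planned and delivered.** SAP 8.1.4.1 specifies it without condition. IA1 follows the last DTH subject's week 4 visit, after every scheduled reading, and Listing 41 carries the raw output. The SAC note is conditional, and SAP 14.9.3 says the list of final outputs will be reviewed. A reader might infer that the hazard ratio is abandoned; the documents support only that a final-analysis version of Table 2.3 would omit it. The IA1 table holds the same unflagged summary, however, and IA1 results have restricted circulation.
- **Unresolved subjects are visible elsewhere.** Listings 38 and 39 and Figure 2.1 show individual data, and the repeated-measures model compares diameters by visit. This helps a careful reader but does not correct the endpoint's own table.
- **The lost days should not be blamed on the missing flag.** A reader might simulate the loss. With log-normal durations (log SD 0.6) and medians of 20 days on placebo and 10 on active, the unrestricted mean difference is 12.0 days against 4.3 recorded. That gap does not measure this defect. Restricted to 20 days with exact times, the difference is 5.6. So 12.0 − 5.6 = 6.4 days reflects the length of follow-up and 5.6 − 4.3 = 1.3 days the visit spacing. With nobody lost early, a Kaplan-Meier restricted mean would return the recorded 4.3.
- **The stakes are modest.** This is one of several secondary endpoints, with 12 subjects and a feasibility-based sample size. That is correct.

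**Conclusion.** The point holds. SAP 8.1.1 scores unresolved reactions as completed, Table 2.3 summarises them that way, and a final version of that table would have no estimate that uses censoring. What is misreported is specific: early losses with strong reactions (7 days in the Day 8 example), non-resolvers who cannot be told from last-visit resolvers (both 21 days on one clock), and a median shown as 21 days when it was not reached.

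A reader might infer that every duration is capped at 21 days and that the drug effect is therefore understated. The SAP as written does not support this: resolvers score 28 to 48 days, and the comparison can reverse. Attenuation describes the plan only after everyone is timed from the re-challenge, and only if more placebo than active subjects stay unresolved. That fits the trial's hypothesis, but no document gives data for it. The sizes shown come from assumed data. The change should be made, because a stated rule gives a misleading secondary-endpoint result and the correction is cheap.

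**What to change.** 1. In SAP 8.1.1 item 3, time every subject from the re-challenge date, and flag as censored any subject not below 6 mm at the last available reading.
2. In Table 2.3, report for each arm the number unresolved and the Kaplan-Meier median, stated as not reached where that applies.
3. Keep the hazard ratio with a 95% CI at the final analysis by deleting the parenthetical exclusion in the table's third note. Compute it on the single clock with the censoring flag, and say so in 8.1.4.1.

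The third change should not be made without the first. The cost is SAP wording and one re-programmed table, with no new data. With 6 v 6 subjects the hazard ratio will be imprecise, and its interval should be read accordingly.
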